**TABLE 2: Composite response criteria** 

Clinical response (digital medical photography)	RECIST 1.1 response (radiolgy)	Composite (overall): clinical + RECIST 1.1 response
Clinical complete response	Complete response or not applicable	Complete response
Not applicable	Complete response	Complete response
Clinical complete response	Partial response or stable disease	Partial response
Clinical partial response	Complete response, partial response, stable disease, or not applicable	Partial response
Not applicable	Partial response	Partial response
Clinical stable disease	Complete response or partial response	Partial response
Clinical stable disease	Stable disease or not applicable	Stable disease
Not applicable	Stable disease	Stable disease
Clinical Progressive disease	Any	Progressive disease
Any	Progressive disease	Progressive disease

### C. Ulcerated Lesions

This section only pertains to target lesions that have extensive ulceration at baseline that prevents measurement by the above methods in this appendix. Response criteria are as follows:

- Complete response: re-epithelialization of the entire baseline area of ulceration of target lesion(s), maintained over at least 4 weeks.
- Partial response: there are no criteria for partial response
- Stable disease: not meeting criteria for complete response or progressive disease
- Progressive disease: new ulceration of target lesion(s) not related to (i.e. in a location separate from) tissue biopsy or other known trauma, persistent without evidence of healing for at least 2 weeks

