#### 2.2 **Primary endpoint**

To assess objective response rate (ORR) of cemiplimab in laBCC at 6 months, by independent central review.

ORR is defined as proportion of patients achieving a complete response (CR) or partial response (PR).

Clinical response criteria (see Appendix 2 table 1) will be used to determine ORR, for externally visible tumour(s) that require bidimensional measurements according to World Health Organization (WHO) criteria. Composite response criteria (see Appendix 2 table 2) will be used for patients who have both target lesions measurable by clinical response criteria and radiologically by RECIST 1.1 to determine ORR.

In patients achieving CR, histological assessment of tumour biopsies will be required to confirm CR, otherwise this will be reported as PR.

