- 6. There must be at least 1 measureable baseline lesion. For visible lesions the longest diameter (LD) and the perpendicular diameter must both be ≥10 mm if followed by digital medical photography. Non-measurable disease for laBCC is defined as either uni-dimensionally measurable lesions, tumours with margins that are not clearly defined, or lesions with maximum perpendicular diameters less than 10 mm. Patients without measureable disease at baseline are not eligible for the study In patients with a deeply invasive lesion that the investigator deems is best measured by magnetic resonance imaging (MRI) or computed tomography (CT), measurement for that target lesion will be done according to RECIST 1.1 criteria. The requirement for a lesion to be measurable by RECIST 1.1 is that it must be ≥10 mm in longest dimension.

If a previously radiated lesion is to be followed as a target lesion, progression must be confirmed by biopsy after radiotherapy. Previously irradiated lesions may be followed as non-target lesions if there is at least 1 other measurable target lesion

- 7. Hepatic function:
  - a. Total bilirubin ≤1.5x upper limit of normal (ULN).
  - b. Patients with Gilbert's Disease and total bilirubin up to 3x ULN are eligible
  - c. Transaminases ≤3x ULN
  - d. Alkaline phosphatase (ALP) ≤2.5x ULN
- 8. Renal function: estimated creatinine clearance
  - >30 mL/min (calculated using the CKD-EPI formula see Appendix 3)
- 9. Bone marrow function:
  - a. Haemoglobin ≥9.0 g/dL
  - b. Absolute neutrophil count (ANC) ≥1.5 x 10^9/L
  - c. Platelet count ≥75 x 109/L

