# 11.1 Sample size calculations

The hedgehog pathway inhibitors (HHIs) have shown an ORR of about 45% in the first line setting. In the ERIVANCE study, the ORR with vismodegib was 42.9% at 9 months follow-up which increased to 47.6% at 21 months follow-up (9). In the BOLT study of sonidegib, the ORR was 47.0% at primary 6 month follow-up, increasing to 56.1% (95% CI: 43.3–68.3) at 18 month follow-up (10). In the second line setting, cemiplimab showed an ORR of 31%, in a recently reported phase 2 study in the 2nd line setting (18), after a median follow-up of 15 months.

Assuming an ORR of cemiplimab to be around 45% at 6-months in the first line setting, this study is powered as a single arm Simon II Stage design. This will be used to differentiate between a poor treatment (success rate of 25%) and a good treatment (success rate 45%) using a nominal significance level alpha = 5% and a power of 80%.

Once 18 patients are recruited, an interim analysis will be performed with the decision rule of progression to Stage II if 6 or more of the 18 patients achieve a response. If ≤5 patients have responded (poor response) or if 15 out of the 18 patients have responded (exceptional response) the trial will be stopped.

Stage II will be the recruitment of a further 19 patients. To account for a potential loss of non-evaluable patients (assuming a 10% drop out rate) the sample size will be inflated to N = 41.

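### The ulcerated-lesion rule in Appendix 2 conflicts with the measurability, biopsy and partial-response rules elsewhere in the protocol, so the response category of such a lesion is not determined

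*Protocol*

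**What the plan says.** **Section C (Protocol, Appendix 2, C. Ulcerated Lesions).** It applies only to target lesions whose baseline ulceration prevents measurement by the methods given earlier in the appendix.
- CR: "Complete response: re-epithelialization of the entire baseline area of ulceration of target lesion(s), maintained over at least 4 weeks".
- PR: "Partial response: there are no criteria for partial response".
- Progression: new ulceration away from a biopsy site or known trauma, not healing for at least 2 weeks.
- SD: everything else.

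**Measurability.** Inclusion criterion 6 (section 4.3) states "Patients without measureable disease at baseline are not eligible for the study" and classes tumours with unclear margins as non-measurable. Section 6.1 requires photographed target lesions to be at least 10 mm in both diameters. Appendix 1 draws target lesions from the measurable ones and makes all others non-target.

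**Biopsy.** Section 2.2 says that for a CR "histological assessment of tumour biopsies will be required to confirm CR, otherwise this will be reported as PR". Section 6.5.1 repeats the rule. Table 1, footnote c, extends the negative-biopsy requirement to any lesion called a clinical CR.

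**Scoring of the primary endpoint.** Section 2.2 defines ORR as CR plus PR. Section 11.3 names Appendix 2, Tables 1 and 2, and does not mention section C. Table 1 takes the categories for externally visible disease, and the clinical column of Table 2 takes the result of Table 1.

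**Ordinary visible progression (Appendix 2, section A).** An increase of at least 25% in the sum of the products of the diameters.

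**The concern.** Section C fixes a response scale that cannot be reconciled with the rules around it, and ORR by independent central review is the primary endpoint.

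1. It presupposes a target lesion that the protocol's own definitions do not allow.
2. It can credit a healed surface as a response with no tumour measurement and no mention of histology. Elsewhere, Appendix 2 (Indeterminate-Appearing Tissue) keeps doubtful tissue in the measurement until a biopsy shows that it is benign.
3. It removes the PR category into which the general rule places a CR without histology.
4. At the level of the lesion, growth is not progression.
5. No rule says how its categories feed Tables 1 and 2, or how an ulcerated target lesion is combined with a measurable one in the same patient.

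At stake is whether such a patient counts as a responder, both at the stage I decision and at the final analysis. The date of progression may also be affected. If the passages are reconciled only once outcomes are known, that is post-hoc adjudication in an open-label, single-arm trial.

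**Working it through.** **Step 1. The stated design reproduces.** Inputs from section 11.1: response rates of 25% (poor) and 45% (good), nominal alpha 5%, power 80%. Stage I has 18 patients and continues "if 6 or more of the 18 patients achieve a response"; "Stage II will be the recruitment of a further 19 patients", so the total is 18 + 19 = 37. The final cut-off is not stated. With X1 ~ Bin(18, p) and X2 ~ Bin(19, p), the probability of success is the sum over x = 6 to 18 of P(X1 = x) × P(X2 ≥ c − x).

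| Final cut-off c | At p = 0.25 | At p = 0.45 |
|---|---|---|
| 13/37 | 0.0876 | 0.852 |
| 14/37 | 0.0496 | 0.806 |
| 15/37 | 0.0249 | 0.732 |

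Only 14/37 meets both targets. No design figure is in dispute. The table shows only where one patient matters: 13/37 = 35.1% against 14/37 = 37.8%.

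**Step 2. One lesion, three readings.** Take a patient whose ulcerated target lesion re-epithelialises for 4 weeks and is not biopsied.

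| Rule followed | Category | In ORR? |
|---|---|---|
| Section C alone | CR | Yes |
| Sections 2.2 and 6.5.1 (no histology, so PR) | PR | Yes |
| Histology rule denies CR and section C denies PR | SD | No |

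Between the first two readings ORR does not change; only the split between CR and PR does. ORR changes only on the third reading. DCR is the same on all three.

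**Step 3. Other routes to a wrong ORR.** Healing over residual tumour would add a responder. A lesion that shrinks substantially without full re-epithelialisation would be SD under section C and could lose a responder. These errors act in opposite directions, so the net bias has no fixed sign.

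**Step 4. Progression.** Growth of a visible ulcerated target lesion without new ulceration is SD under section C. The patient can still progress through a new lesion (Appendix 2, section B), unequivocal non-target progression (section A) or RECIST progression (Table 2). The gap is therefore growth of a visible ulcerated target lesion that is not followed radiologically. There DCR and PFS may be overstated. The documents do not allow this to be quantified.

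**Step 5. Size per misclassified patient.** 1/37 = 2.7 points at the end and 1/18 = 5.6 points at stage I, where the decision turns on 5 against 6 responders. The probability of exactly 5 or 6 responses among 18 is 0.199 + 0.144 = 0.34 at a true rate of 25%, and 0.067 + 0.118 = 0.18 at 45%. In those cases one misclassification in the relevant direction reverses the decision.

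**Step 6. Illustration under assumed frequencies.** The protocol gives none of these inputs. Let f be the share of patients scored under section C.
- *Over-count.* A share g of their true non-responders is scored CR, so the effective null rate is 0.25 + f × g × 0.75. With f = 5%, g = 10% it is 0.254 and alpha is 0.055. With f = 20%, g = 30% it is 0.295 and alpha is 0.153.
- *Under-count.* A share h of their true responders is lost for want of a PR category, so the effective rate is 0.45 × (1 − f × h). With f = 5%, h = 25% it is 0.444 and power is 0.79. With f = 20%, h = 75% it is 0.3825 and power is 0.53.

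**The case against.** Section C is silent on biopsy; it does not waive it. The general rule covers every CR, and its ordinary consequence is PR, which still counts in ORR. A reader might infer that section C grants CR on skin healing alone and so inflates ORR. The documents do not support that: on the plain reading of section 2.2 the biopsy conflict shifts ORR by zero.

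A reader might also infer that a patient with only such a lesion can properly enter and become a responder without any tumour measurement. Criterion 6 already excludes a patient whose only lesion can be measured neither by photography nor by RECIST 1.1. An eligible patient therefore has another measurable lesion.

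Nor is it right that such a patient can progress only by new ulceration or can never reach PR. Step 4 of the working lists the other progression routes. For PR, Table 2 turns clinical SD with a RECIST PR into PR, and Appendix 2 counts surgery with clear margins on lesions rendered operable as PR. Headings A to D can also be read as one series of clinical criteria, with the tables merely placed between B and C, and central review sees the photographs and biopsy results.

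All of this stands, and it narrows the point. It does not settle which category an unbiopsied healed ulcer receives, how an ulcerated and a measurable target lesion combine in one patient, or how growth of an ulcerated target lesion without radiological follow-up is scored.

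**Conclusion.** The conflict is real and worth correcting: the protocol does not determine the response category of a target lesion scored under section C. The measurability conflict concerns what a target lesion is; it does not open a route into the trial.

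The size is 2.7 points of ORR per misclassified patient among 37, or 5.6 points among 18. This holds for a patient who is misclassified, not for every patient scored on this scale. The number of such patients is not given and may be zero. The direction of the ORR error is not fixed. DCR and PFS may be overstated, but only through the growth gap. The alpha and power ranges in the working rest entirely on assumed frequencies; they show sensitivity and are not estimates for this trial.

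**What to change.** **Preferred change.** State in Appendix 2 that a lesion too ulcerated to be measured by photography or by RECIST 1.1 is not a target lesion, does not satisfy inclusion criterion 6, and is followed as non-target. Sections 4.3 and 6.1 and Appendix 1 already imply this.

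**If section C is kept.**
- State that the existing biopsy requirement applies to it, and which category a healed ulcer without a biopsy receives, in agreement with sections 2.2 and 6.5.1 and Table 1, footnote c.
- Reconcile its progression wording with section A of the same appendix. No new progression threshold is proposed: the lesion is by definition unmeasurable, and progression bears on stopping treatment (section 9.1).
- State how its categories enter Tables 1 and 2, including when the patient also has a measurable target lesion.

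**Cost.** Amendment wording only, with no additional procedure, since the biopsy is already required for CR. The downside is that a few heavily ulcerated lesions no longer contribute as target lesions. Patients with no other measurable lesion are not enrolled, as criterion 6 already provides.

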## D. Non-Target Lesions

Measurements of non-target lesions are not required. The presence, absence, or in rare cases unequivocal progression of these lesions should be noted throughout follow up.

### **APPENDIX 3: MEASUREMENT OF eGFR**

Estimated GFR is required. One of the following 3 methods is allowed.

- 1. The recommended technique is eGFR calculated using the CKD-EPI formula according to the table below
- 2. By accessing the online calculator for the CKD-EPI GFR calculation at http://www.qxmd.com/calculate-online/nephrology/ckd-epi-egfr
- 3. Modified Cockcroft and Gault

Race and Sex	Serum Creatinine	Equation
	Level, µmol/L (mg/dl)	·
Black		
Female	≤62 (≤0.7)	GFR = $166 \times (SCr/0.7)^{-0.329} \times (0.993)^{Age}$
	>62 (>0.7)	$GFR = 166 \times (SCr/0.7)^{-1.209} \times (0.993)^{Age}$
Male	≤80 (≤0.9)	GFR = $163 \times (SCr/0.9)^{-0.411} \times (0.993)^{Age}$
	>80 (>0.9)	GFR = $163 \times (SCr/0.9)^{-1.209} \times (0.993)^{Age}$
White or other		
Female	≤62 (≤0.7)	$GFR = 144 \times (SCr/0.7)^{-0.329} \times (0.993)^{Age}$
	>62 (>0.7)	$GFR = 144 \times (SCr/0.7)^{-1.209} \times (0.993)^{Age}$
Male	≤80 (≤0.9)	GFR = $141 \times (SCr/0.7)^{-0.411} \times (0.993)^{Age}$
	>80 (>0.9)	$GFR = 141 \times (SCr/0.7)^{-1.209} \times (0.993)^{Age}$

For patients with borderline renal function (CKD-EPI formula produces a result that is lower than 60ml/min) a direct measurement of GFR as per standard of care at the patient's institution is recommended. A result of >60ml/min from this method should be regarded as the more accurate estimate.

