#### 6 STUDY PROCEDURES AND EVALUATIONS

#### 6.1 **Baseline** (within 7 days of registration)

Patients will undergo general assessment and assessment of their disease to include:

- Physical examination to assess fitness (including height and weight); ECOG performance status; vital signs (blood pressure, heart rate, oxygen saturation, temperature).
- Recording of concomitant medication use, with relevant dates.
- Medial and cancer history.
- ECG.
- Photography of skin lesion(s), including those to be followed as target lesions within 6 weeks of scheduled start date of immunotherapy. Target lesions need to be ≥10mm in both the longest diameter and the perpendicular diameter.
- MRI/ CT scan (with IV contrast) of the area encompassing the primary tumour (e.g. head and neck, chest, abdomen etc) to be performed within 6 weeks of scheduled start date of immunotherapy. If the lesions are in the head and neck region an MRI scan would be preferred. This scan will document any deeper extent of disease and whether this modality will be used to follow any target lesion(s). The same modality used to document target lesion extent at baseline must be used throughout the study.
- Full blood count, U+Es (including urea, sodium, potassium, total calcium and creatinine), liver function tests (to include ALP, ALT, Albumin and Bilirubin), LDH, thyroid function tests (including TSH, T4 and if required T3), cortisol and glucose (random). NB cortisol levels need to be measured ideally before 9am.
- Viral screen to include HIV, Hepatitis B and Hepatitis C. Patients with well controlled HIV will need to show undetectable viral load and CD4 counts over 350 to confirm inclusion into the study.
- Serum pregnancy test if required
- Estimated GFR to be assessed according to local practice (recommended technique of eGFR using the CKD-EPI formula (see Appendix 3)).
- Baseline assessment of symptoms using common toxicity scoring (CTCAE v5.0).
- Completion of Quality of life questionnaires EQ-5D-5L, EORTC QLQ-C30, Skindex-16, FNAE and the Hornheide questionnaire.

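### Criterion 8 fixes CKD-EPI for the 30 mL/min entry limit, but Appendix 3 and section 6.1 admit a different, unprinted method, so entry near the limit can depend on the method used

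*Protocol*

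**What the plan says.** Criterion 8 in section 4.3 is headed "Renal function: estimated creatinine clearance" and sets the limit at more than 30 mL/min, "calculated using the CKD-EPI formula see Appendix 3".

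Appendix 3, to which the criterion refers, opens with "One of the following 3 methods is allowed". The first method is introduced with "The recommended technique is eGFR calculated using the CKD-EPI formula according to the table below". The second is an online calculator for CKD-EPI. The third is given by name only: "Modified Cockcroft and Gault". No equation, weight basis or meaning of the modification is printed for it.

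Section 6.1, which lists the baseline assessments, says "Estimated GFR to be assessed according to local practice" and adds CKD-EPI as a recommendation.

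Appendix 3 also recommends a direct GFR measurement at the institution when CKD-EPI gives less than 60 mL/min. A direct result above 60 is to be taken as the more accurate one. Nothing is said about a direct result of 60 or lower.

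**The concern.** An entry limit should give each patient one value to compare with one number. Here the criterion names one formula, the appendix it cites permits another, and the baseline procedure defers to the site. A site can do exactly what section 6.1 and Appendix 3 allow and still not have applied criterion 8 as written. For a patient near 30 mL/min, the answer to whether the patient may enter can then differ with the method.

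At stake are avoidable eligibility deviations and uneven entry across centres in a multi-centre trial of 41 patients. This is an eligibility rule, so it belongs in the protocol and cannot be left to a statistical analysis plan.

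**Working it through.** The plan states no figure on this point, so there is none to reproduce. The check compares the passages and then illustrates the effect.

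**1. The three places side by side**

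| Place | Status of CKD-EPI | Other method open? |
|---|---|---|
| Section 4.3, criterion 8 | Required for the >30 mL/min limit | No, but refers to Appendix 3 |
| Section 6.1, baseline | Recommended | Yes, local practice |
| Appendix 3 | Recommended | Yes, method 3 |

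**2. Where the conflict lies.** Methods 1 and 2 are nominally one formula, as a table and as a calculator. Only method 3 departs from criterion 8.

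**3. Does any text keep method 3 out of the eligibility decision?** No. Appendix 3 does not confine it to monitoring. The baseline wording (section 6.1) and the on-treatment wording (section 6.2) are nearly identical: CKD-EPI is the recommended technique in one and the preferred technique in the other.

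**4. Illustration near the limit.** The printed row for White or other women with creatinine above 0.7 mg/dL is 144 × (SCr/0.7)^−1.209 × 0.993^age. No Cockcroft-Gault equation is printed, so the ordinary form is *assumed*: (140 − age) × weight × 0.85 / (72 × SCr) for women. Take age 80, where 0.993^80 = 0.570.

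- SCr 1.5: CKD-EPI = 144 × (1.5/0.7)^−1.209 × 0.570 = 32.7, which passes. Cockcroft-Gault = 60 × weight × 0.85 / 108, giving 23.6 at 50 kg and 28.3 at 60 kg (both fail) and 33.1 at 70 kg (passes).
- SCr 1.8: CKD-EPI = 144 × (1.8/0.7)^−1.209 × 0.570 = 26.2, which fails. Cockcroft-Gault = 60 × weight × 0.85 / 129.6, giving 27.5 at 70 kg (fails), and 31.5 at 80 kg and 39.4 at 100 kg (both pass).

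Under this assumption the decision can flip in either direction. The permitted method is a modified version, so these values need not describe it.

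**5. The printed CKD-EPI table.** For White or other men the creatinine cut-point is 0.9 mg/dL but both rows divide by 0.7. The rows for Black men have the same cut-point and divide by 0.9. At SCr 0.9, before the age factor, the two White-or-other male rows give:

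- lower row: 141 × (0.9/0.7)^−0.411 = 127.2
- upper row: 141 × (0.9/0.7)^−1.209 = 104.1

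The function therefore jumps at its own cut-point. Above it, the printed value is (0.7/0.9)^1.209 = 0.738 times the value with 0.9. For a 70-year-old man with SCr 1.8, that is 27.5 as printed against 37.3 with 0.9, on opposite sides of the limit.

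**6. Direct measurement.** Every patient near 30 by CKD-EPI is below 60, so the recommendation to measure GFR directly applies to all of them. How a direct result of, say, 35 bears on the limit of 30 is not stated.

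**The case against.** The best reply is that the specific criterion governs entry. Appendix 3 is a general appendix that also serves visits at which no 30 mL/min limit applies, and section 6.1 itself recommends CKD-EPI. That reading is reasonable, but no sentence states it. Criterion 8 sends the reader to the appendix, and section 6.1 is the baseline assessment. The inconsistency stands.

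A reader might infer that the same patient will be accepted at one site and refused at another, or that sites may freely pick whichever method admits a patient. The documents do not support this. Under section 5, one central team confirms eligibility from a checklist before registration. What renal detail the checklist carries is not shown, so this control may catch some cases but cannot be counted on for all. Nor can the choice be called legitimate and its result a violation at once: that depends on which passage prevails, and this is the unresolved point.

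A reader might also infer an effect on the trial's result. None follows. The dose is fixed with no reductions (sections 7.1 and 7.5.1), the renal toxicity rules in Appendix 5 use change in creatinine, no endpoint uses eGFR, and section 11.2 specifies intention to treat.

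Finally, the Cockcroft-Gault figures rest on an assumed, unmodified formula. That is correct, and they are illustrative only. The textual conflict does not depend on them.

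**Conclusion.** The contradiction is on the page and is minor. Criterion 8 fixes CKD-EPI; Appendix 3 and section 6.1 leave room for a different method whose equation is not given. Entry can depend on the method only for patients near the limit, and the documents do not say how many there will be. Sample size, error rates and the primary analysis are untouched.

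Two related faults in Appendix 3 matter for the same decision: the inconsistent divisor in the White-or-other male rows, and the unfinished rule on direct measurement. The first should be checked against the source of the table before it is called a misprint. Both mean that aligning the three places on the table as it stands would not be enough. Which renal method or threshold is right is for the sponsor to decide.

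**What to change.** 1. Reconcile criterion 8, section 6.1 and Appendix 3 so that all three name the same single method for the eligibility decision, with its equation printed. Use one term for the quantity: criterion 8 speaks of creatinine clearance but cites a formula that returns a GFR.
2. If another method is kept, limit it to on-treatment monitoring and print its formula.
3. Check the divisor in the two White-or-other male rows of the CKD-EPI table against the 0.9 cut-point and the rows for Black men.
4. State how a direct GFR result of 60 mL/min or lower bears on the limit of 30.
5. In the same edit, correct the 3 month safety visit in section 6.4, which points to Appendix 2 for the CKD-EPI formula.

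The cost is an amendment of wording. Creatinine, age and sex are already available, and no sample size or analysis changes.

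### Appendix 3 divides creatinine by 0.7 instead of 0.9 in both White/other male rows, so the printed table understates eGFR and can wrongly fail men on the >30 mL/min criterion

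*Protocol*

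**What the plan says.** Section 4.3, criterion 8, sets the renal limit at ">30 mL/min (calculated using the CKD-EPI formula see Appendix 3".

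Appendix 3 allows three methods: the printed table, an online CKD-EPI calculator and modified Cockcroft and Gault. It puts the table first: "The recommended technique is eGFR calculated using the CKD-EPI formula according to the table below". Below a CKD-EPI result of 60 mL/min it recommends a direct GFR measurement, and it says that a direct result above 60 is the more accurate one.

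The table has a low-creatinine and a high-creatinine row for each of four race and sex groups. The break-point is 0.7 mg/dL (62 µmol/L) for women and 0.9 mg/dL (80 µmol/L) for men. The male rows read:

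- Black men, up to 0.9: "163 \times (SCr/0.9)^{-0.411} \times (0.993)^{Age"
- Black men, above 0.9: "163 \times (SCr/0.9)^{-1.209} \times (0.993)^{Age"
- White/other men, up to 0.9: "141 \times (SCr/0.7)^{-0.411} \times (0.993)^{Age"
- White/other men, above 0.9: "141 \times (SCr/0.7)^{-1.209} \times (0.993)^{Age"

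Sections 6.1 to 6.4 also call for eGFR at baseline, before each cycle, at end of treatment and at the 3-month visit. They leave the technique to local practice and name CKD-EPI as recommended or preferred.

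**The concern.** The two male groups share a break-point and both exponents, yet one divides by 0.9 and the other by 0.7. A two-branch formula of this kind joins up only when the divisor equals the break-point, so the White/other male rows cannot be right as a pair.

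A larger creatinine ratio raised to a negative power gives a smaller eGFR, so the printed rows understate renal function in this group. Because criterion 8 relies on this appendix, the group would in effect face a stricter renal limit than the protocol states. Section 4.1 calls locally advanced BCC rare and the target is 41 patients, so an eligible man turned away for a table error is a real loss to recruitment.

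**Working it through.** **Inputs**, all from the Appendix 3 table. Each row has the form c × (SCr/k)^−e × 0.993^Age, with SCr in mg/dL. On the low branch e is 0.329 for women and 0.411 for men; on the high branch e is 1.209 for everyone.

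**Step 1: do the branches meet?** Put SCr equal to the break-point and leave out the age factor, which both branches share.

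| Group | Break-point | Divisor k | Low branch | High branch |
|---|---|---|---|---|
| Black female | 0.7 | 0.7 | 166.0 | 166.0 |
| Black male | 0.9 | 0.9 | 163.0 | 163.0 |
| White/other female | 0.7 | 0.7 | 144.0 | 144.0 |
| White/other male, as printed | 0.9 | 0.7 | 141 × (0.9/0.7)^−0.411 = 127.2 | 141 × (0.9/0.7)^−1.209 = 104.1 |
| White/other male, divisor 0.9 | 0.9 | 0.9 | 141.0 | 141.0 |

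The table reproduces itself in three groups. In the fourth, eGFR drops by 18.2% at a single creatinine value.

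**Step 2: is the divisor or the break-point the odd one out?** Two checks point to the divisor.

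- The break-point is given in two units that agree: 80/0.9 = 88.9 µmol/L per mg/dL, against 62/0.7 = 88.6 in the female rows. A male break-point of 0.7 would not fit 80 µmol/L (80/0.7 = 114.3).
- The ratio of Black to White/other is 166/144 = 1.153 in women. In men it is 163/141 = 1.156 if the divisors are equal. As printed it becomes 1.156/0.738 = 1.566 on the high branch and 1.156/0.902 = 1.282 on the low branch.

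**Step 3: size of the error.** Printed value over 0.9-divisor value depends only on the exponent, not on age or creatinine:

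- above 0.9 mg/dL: (0.7/0.9)^1.209 = 0.738, so 26.2% too low;
- at or below 0.9 mg/dL: (0.7/0.9)^0.411 = 0.902, so 9.8% too low.

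**Step 4: who is affected at the limits?**

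- Criterion 8: a printed 30 corresponds to 30/0.738 = 40.7. Men above 30 and up to 40.7 with the 0.9 divisor compute as 30 or less. They are all on the high branch, so the full 26.2% applies.
- Trigger for direct measurement: 60/0.738 = 81.3. Men from 60 to 81.3 compute as below 60. Above about age 78 the range ends slightly lower, because eGFR at the break-point is itself below 81.3 (141 × 0.993^80 = 80.4 at age 80). The low branch would matter only below 60/0.902 = 66.5, which it does not reach before about age 107.

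**Step 5: examples.**

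| Age, SCr | As printed | Divisor 0.9 |
|---|---|---|
| 75 y, 1.7 mg/dL | 141 × (1.7/0.7)^−1.209 × 0.993^75 = 28.5 | 38.6 |
| 70 y, 1.8 mg/dL | 27.5 | 37.3 |

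Both men fail criterion 8 on the printed row and pass with the 0.9 divisor. At age 70 the creatinine at which eGFR equals 30 moves from 1.68 mg/dL as printed to 2.16 mg/dL.

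**The case against.** The strongest case against concedes the inconsistency and disputes the consequences.

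- **The table need not be used.** The online calculator and modified Cockcroft and Gault do not use these rows, sections 6.1 and 6.2 defer to local practice, and the online calculator also fits the wording of criterion 8. This stands. A reader might infer that eligible patients are being excluded; the protocol supports only that they can be, at sites that compute from the printed table.
- **Direct measurement is a safeguard.** Every man in the 30 to 40.7 range is below 60 with either divisor, so direct measurement is already recommended for him. This stands in part. It is a recommendation, and precedence is stated only for a direct result above 60, so a man measured at, say, 36 is not clearly rescued.
- **Treatment is not affected.** A reader might infer from the pre-cycle eGFR checks that the error reaches dosing decisions. It does not: the delay and discontinuation rules in sections 7.5.2 and 7.5.4 contain no eGFR threshold, and the renal guidance in Appendix 5 works from creatinine.
- **The error runs one way.** It understates renal function, so it admits nobody below the stated limit. This stands and lowers the severity.
- **The text was machine-read and the cited equation is not at hand.** A misreading is unlikely, since 0.7 appears in both White/other male rows while 0.9 was read in the Black male rows and in every male break-point. The original page should still be checked.

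**Conclusion.** The point holds as an error in the table, shown by the table alone. Relative to its own 0.9 mg/dL break-point, the printed White/other male rows are 26.2% too low above 0.9 mg/dL and 9.8% too low at or below it. The range at risk of a wrong failure on criterion 8 is above 30 and up to 40.7 mL/min; the range at risk of needless direct measurement is 60 to 81.3 mL/min.

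This assumes that the break-point is right and the divisor wrong, which both checks in Step 2 support, and that the site computes from the printed table. How many patients that covers cannot be derived from the protocol.

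The consequence is limited to eligibility and extra testing. The primary endpoint, the sample size and the stage decision rule do not depend on eGFR, so it is a should-fix and not a threat to the trial's conclusions.

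**What to change.** In Appendix 3, change the divisor from 0.7 to 0.9 in both White/other male rows, so that it equals the break-point as in every other group. Before issuing the change, check both rows against the original page and the cited equation. Confirm also that the corrected table and the online calculator listed as the second method agree for a few test values, such as the two examples above.

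Re-check any renal screen failures among White/other men whose eGFR was computed from the printed table. The 30 mL/min limit itself is not in question.

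The cost is two table cells in the next amendment, a short note to sites and a review of renal screen failures.
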